from linear regression to mixed-effect models to complicated mediation analyses, all using the same state-of-the-art optimization and data handling methods. For example, prelinguistic communication skills are measured both: (a) continuously during intervention (via a language sample) and (b) after intervention (via the CSBS). As such, analysis of the effects of intervention on prelinguistic skills features two similar analyses: a latent growth curve of the monthly language sample (analysis 1.2a) and a linear regression for CSBS scores (analysis 1.2b). These two analyses answer similar questions (e.g., what is the direct effect of intervention on child prelinguistic skills) that differ based on the data on which they depend. Analysis 1.2a predicts month-to-month growth in child prelinguistic communicative acts, while 1.2b predicts a single CSBS score. These two modeling frameworks vary in their complexity and their modeling assumptions, specifically that latent growth curves estimated via SEM have more robust missing data handling than conventional regression software that requires complete cases. Estimating all models as SEMs means that all models retain the same underlying full sample sizes and assumptions, so that disparate results can be more directly attributed to constructs. In this example, stronger effects on monthly prelinguistic skills would reflect more proximal effects of intervention rather than a weakness of conventional regression methods and their missing data assumptions.

Data reduction of primary outcomes. Our multi-method approach requires data reduction and integration within and across time points. We will create a set of continuous latent indicators of child prelinguistic communication, child spoken language outcomes and parent use of communication support strategies. We will create these latent indicators using confirmatory item factor analyses, which allow us to combine the categorical data handling of an item response model with the flexibility to incorporate multidimensionality and specific measurement hypotheses common to factor analyses. We will further use multi-trait, multi-method approaches and related bifactor models when constructs span multiple modes of assessment (observational, elicited, parent report). See Table 1 for a summary of primary outcome constructs.

Table 1. Primary outcome constructs by analysis					
Construct	Measurement Structure	Measures	Variables Extracted	Measurement Occasions	Variable Type by Analyses

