Power for tests of intervention effects were estimated using G*Power⁹⁵ supplemented with custom simulations to verify accuracy and tailor assumptions to our research design. Given a sample size of 86 (96 recruited participants with 10% attrition), we project greater than 99% power for main effects of the intervention (aim 1) as large as those shown in our pilot study (d=1.07) (see Justification and Feasibility in Research Strategy). We further project 80% power for effects as low as d=.61 and 90% for d=.71. Each of the three previous estimates assume control for pre-test and 10% attrition (e.g., n=86). Our research group has maintained greater than 95% retention in comparable studies over the last two years. We would retain power for smaller effect sizes of d=.58 (80% power, down from d=.61) and d=.67 (90% power, down from d=.71) if no attrition occurs.

The above power analysis covers the primary analyses for Aims 1 and 3. However, these aims also include growth in parent and child outcomes assessed monthly. These analyses depend on latent growth curve models, as described above and require a simulation-based power estimate, as described in Zhang & Wang (2009). We simulated our monthly assessments four thousand times, varying our predicted effect size and distribution of latent intercepts and slopes. This simulation yielded reliable power estimates for each effect size. The use of longitudinal data yield improved power over our simple pre-test-post-test designs in the previous paragraph. We project 80% power for d=.34, and 90% for d=.45. Furthermore, we have 80% power to detect moderators (aim 2) that account for 7.8% of variance in the outcome or greater, and 90% for 10.4% of variance. In summary, this study is well-powered to test the effects of intervention on parent and child outcomes.

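### A stronger monthly result (1.2a) than CSBS result (1.2b) cannot be read as a more proximal effect merely because both models share sample and missing-data handling

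*SAP*

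**What the plan says.** The Structural Equation Modeling paragraph of the SAP's Overview pairs two analyses of child prelinguistic skills: "a latent growth curve of the monthly language sample (analysis 1.2a) and a linear regression for CSBS scores (analysis 1.2b"). It treats them as addressing similar questions with different data. Because all models are fitted as SEMs with full information maximum likelihood (FIML), it says they keep the same sample and assumptions, "so that disparate results can be more directly attributed to constructs". It then gives its reading of one possible outcome: "stronger effects on monthly prelinguistic skills would reflect more proximal effects of intervention rather than a weakness of conventional regression methods". The sentence goes on to name missing-data assumptions, so the rival explanation it sets aside is complete-case regression.

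SAP Table 1 lists the 1.2a outcome as latent, with six time points between pre and post, and the 1.2b outcome as observed, at post only. The Power Analysis section says: "The use of longitudinal data yield improved power over our simple pre-test-post-test designs in the previous paragraph". The SAP does not define what makes one effect stronger than another, and it contains no test of the difference between the two effects.

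**The concern.** A shared sample and shared missing-data handling remove one reason why 1.2a and 1.2b might disagree. They leave at least two others: the analyses have different precision, and the single CSBS score carries measurement error that a latent slope is meant to separate out. Either can make the monthly result look stronger when the intervention affects both outcomes equally.

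At stake is the interpretation of Aim 1. A report that followed the illustration could describe an effect on proximal behaviour that does not carry over to overall prelinguistic skill, when the data cannot separate that from unequal precision.

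**Working it through.** **Inputs.** From the SAP's Power Analysis:
- Sample size: "Given a sample size of 86 (96 recruited participants with 10% attrition").
- Single-score analysis: "We further project 80% power for effects as low as d=.61 and 90% for d=.71".
- Adjustment: "Each of the three previous estimates assume control for pre-test and 10% attrition (e.g., n=86"). No pre-post correlation is given.
- Growth analysis: 80% power at d=.34 and 90% at d=.45, from a simulation whose inputs are not reported. These are taken as stated.

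Assumed, because not stated: two-sided alpha .05 and 1:1 allocation (43 per group).

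**Step 1: reproduce the plan's figure.** Two-sample t-test, 84 degrees of freedom, noncentrality d × √(43×43/86) = 4.637d, no variance reduction from pre-test. Power is 79.8% at d=.61, 90.2% at d=.71 and 99.8% at d=1.07. The single-score figures therefore reproduce, but with no gain from pre-test adjustment.

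**Step 2: power of 1.2b at the growth-curve effect sizes.** The same formula gives 34.4% at d=.34 and 54.1% at d=.45.

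**Step 3: chance that 1.2a is significant and 1.2b is not, with equal true d.** Let A and B be the two powers. If the tests are nested (1.2b is significant only when 1.2a is), the chance is A − B. If independent, it is A(1 − B).

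| True d | A | B | Nested | Independent |
|---|---|---|---|---|
| .34 | .80 | .344 | .80−.344 = 46% | .80×.656 = 52% |
| .45 | .90 | .541 | .90−.541 = 36% | .90×.459 = 41% |

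At d=1.07 B is .998, so the chance is about 0.2%.

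**Step 4: let pre-test adjustment help 1.2b.** With an assumed pre-post correlation r, replace d by d/√(1−r²). At d=.34, B becomes 43.6% (r=.5) or 58.8% (r=.7). With independent tests the pattern is .80×.564 = 45% or .80×.412 = 33%.

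**Step 5: put d in slope-SD units.** With 43 children per group, extra waves remove occasion error but not differences between children. Without adjustment, even a perfectly measured slope has the Step 2 power: 34.4% at d=.34 and 54.1% at d=.45. Assume CSBS reliability of .7 to .9, so its observed d shrinks by √.7=.84 to √.9=.95.
- d=.34: B is 25.6% to 31.5%. Nested 3-9%, independent 24-26%.
- d=.45: B is 40.8% to 49.9%. Nested 4-13%, independent 27-32%. The reverse pattern (1.2b significant, 1.2a not) is then 19-23% with independent tests.

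**Step 6: read stronger as a larger point estimate.** With equal true effects on one scale, 1.2a is larger half the time by symmetry, whatever the power. The implied standard errors are .34/2.80=.121 for 1.2a and 2/√86=.216 for 1.2b. The difference then has SD .247 if the estimates are independent and .187 at correlation .5, so 1.2a leads by more than 0.2 in about 21% or 14% of trials.

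**Check on the stated pair.** Under a normal approximation, d at 90% over d at 80% should be 3.24/2.80=1.16; the SAP's .45/.34 is 1.32. Anchoring on .45 at 90% puts power at d=.34 near 69%, and the Step 3 range at d=.34 becomes .69−.344 = 34% to .69×.656 = 45%.

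**The case against.** The strongest reply is that there is no rule here to follow. The sentence is an example in an overview paragraph on why one estimation framework is used; its full wording is aimed at the complete-case artefact, and the companion sentence is hedged. The Aim 1 analytic plan tests each outcome against control and never compares 1.2a with 1.2b. This stands. A reader might infer that the SAP binds itself to a decision rule, or that Aim 1's efficacy conclusions are in danger; the documents support neither.

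Second, the text speaks of stronger effects, not of significance in one analysis and not the other. The Step 3 percentages apply only to the significance reading. On the point-estimate reading, the power figures do not drive the result.

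Third, the SAP does not define d for a slope, or say whether .34 and .45 belong to the Aim 1 series or the longer Aim 3 series. A reader might infer that more measurements and better reliability alone explain .34 against .61. That is not shown: without a different scale, it would take conditioning worth 1−(.34/.61)²=.69 of the variance, a correlation of about .83. Step 5 shows how much smaller the asymmetry becomes on a slope-SD scale.

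What survives is narrower. The paragraph names one rival explanation, omits unequal precision, which the same SAP reports elsewhere, and offers no comparison that could support the attribution.

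**Conclusion.** The concern holds as a flaw in a stated interpretation. Common FIML estimation does not license attributing a 1.2a-1.2b difference to construct or proximity. How often the misleading significance pattern would arise with equal true effects depends on assumptions the SAP leaves open:
- 46-52% at d=.34 and 36-41% at d=.45, if the stated d values share one scale and pre-test adjustment gives 1.2b nothing;
- 33-45% at d=.34, if adjustment helps with r of .7 to .5 and the tests are independent;
- about 3-32% across d=.34 and .45, if d is in slope-SD units and CSBS reliability is .7 to .9;
- about 0.2% at the pilot effect.

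The upper figures are therefore conditional, not a general error rate. The matter deserves correction because the pattern can be common at the effect sizes the growth analysis is powered for, and because the remedy is cheap.

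**What to change.** Replace the illustrative sentence with wording such as:

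> Common FIML estimation removes differences in missing-data handling only. A difference between 1.2a and 1.2b, including significance in one and not the other, will not be attributed to construct or proximity unless both effects are put on a pre-defined common standardised scale, estimated in one joint model, and their difference has a 95% confidence interval excluding zero. Measurement error in the single CSBS score will be noted as an alternative explanation. Otherwise the difference and its interval are reported as inconclusive.

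Two details matter. A non-significant difference must not be reported as agreement. Standardising by itself does not remove measurement error from the CSBS score, so that caveat stays even when the interval excludes zero.

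The cost is SAP wording plus one bivariate model, since 1.2a and 1.2b are specified separately. Protocol Table 1 already schedules the language sample (T0 and monthly) and the CSBS (T0 and T7), so no new data are needed. With 86 to 96 children the contrast will be imprecise, and inconclusive may be the usual answer. The separate tests of 1.2a and 1.2b against control do not change.

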Parent Use of Communication Support Strategies	Latent	Parent use of communication support strategies coded from a parent-child interaction	The following measures from the coded parent-child interaction sample: Percentage of intervals in which the adult is	Monthly from 12 to 18 months of age (6 time points between pre and post)	Analysis 1.1: Dependent Analysis 2.1: Dependent Analysis 4.1a: Mediator Analysis 4.1b: Mediator
			communicating within the child's line of sight Percentage of adult communication that is paired with a gesture in the child's line of sight Percentage of intervals in which the adult's play is related and is in close proximity to the child Percentage of child nonverbal actions that are mirrored and mapped Percentage of child communication that is followed by a contingent response Percentage of adult communication that is in response to child communication Percentage of adult communication Percentage of adult communication that contains a child linguistic target Percentage of child communication to which the adult imitates and adds a word	Monthly from 18 to 36 months of age (18 time points between post and follow-up)	Analysis 3.1: Dependent Analysis 4.2a: Mediator Analysis 4.2b: Mediator
Child Prelinguistic Communicative Acts	Latent	Language Sample	Number of child prelinguistic communicative acts coded from the language sample	12 to 18 months of age (6 time points between pre and post)	 Analysis 1.2a: Dependent Analysis 2.2a: Dependent Analysis 2.3a: Dependent Analysis 4.1a: Dependent Analysis 4.3a: Mediator
Child Overall Prelinguistic Skills	Observed	Communication and Symbolic Behavior Scale (CSBS)	Total Scaled Score	At 18 months of age (post)	 Analysis 1.2b: Dependent Analysis 2.2b: Dependent Analysis 2.3b: Dependent Analysis 4.1b: Dependent Analysis 4.3a: Mediator Analysis 4.3b: Mediator
Child spoken words	Latent	MacArthur-Bates Communicative Development Inventory; Language Sample	Total number of Words Said from the MacArthur- Bates Communicative Development Inventory Total number of different spoken word roots from the language sample	18 to 36 months of age (18 time points between post and follow-up)	 Analysis 3.2a: Dependent Analysis 4.2a: Dependent Analysis 4.3a: Dependent
Child overall spoken language	Observed	Preschool Language Scale-5 th Edition	Total Standard Score	At 36 months of age (follow-up)	Analysis 3.2b: DependentAnalysis 4.2b: DependentAnalysis 4.3b: Dependent

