Covariates. Controlling for covariates is an important part of any analysis. While randomization and stratification should remove effects of these variables, additional statistical control curtails potential unhappy randomizations and other threats to internal validity. As such, we will examine differences between experimental conditions for the following variables: non-verbal cognitive skills, degree of hearing loss in the better ear, hearing age, hours of hearing device use, SES, sign exposure in the home, other spoken languages in the home and amount of community-based early intervention therapy services. Should a difference exist at any point in the study, we will include that variable in all statistical analyses.

Multiple testing. Our proposed analyses and rich multivariate data collection will allow us to test hypotheses in multiple ways. Our focus on SEM will allow for complex hypotheses to be tested with a single model, obviating part of the need for multiple testing corrections. However, we will further employ Benjamini-Hochberg corrections⁸⁸ as needed to correct for multiple testing. This procedure is a more sophisticated alternative to traditional Bonferroni corrections that better account for multiple simultaneous significant parameters.

[figure not shown]
Aim 1 Analyses

This aim tests the main effects of the intervention, both on parental use of communication support strategies and on child prelinguistic skills. We predict that: (a) parents in the intervention group will use more communication support strategies during intervention than parents in the control group (analysis 1.1); (b) children in the intervention group will have greater growth in rate of prelinguistic communicative acts between 12 months (pre) and 18 months of age (post) (analysis 1.2a) and greater overall prelinguistic skills at 18 months of age (post) (analysis 1.2b) than children in the control group. We will employ a mix of traditional and advanced statistical methods, balancing simplicity of linear regression and related methods with sophisticated SEMs that handle attrition and missing data and allow for more flexible integration of time-varying covariates.

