One example of a latent growth curve model is shown in Figure 2, where latent intercepts (level) and slopes (indicated by the circles labeled " L_c " and " S_c ") represent unmeasured variables that describe how children differ from each other in their overall level of prelinguistic development. These two latent variables predict and describe how children grow in their prelinguistic communicative abilities from age 12 months (C_{12}) to age 18 months (C_{18}). Latent growth models will be used for analyses 1.1 and 1.2a, all of which use a slope factor as a dependent variable.

Aim 1 analytic plan. Analyses for Aim 1 will utilize SEM equivalencies of both traditional regressions and growth curve extensions of these models. We will estimate all models in SEM to minimize the impact of attrition.

Analysis 1.1. Intervention will predict the slope factor in a latent growth curve model of overall parent use of communication support strategies, which is a latent variable of parent use of communication support strategies estimated monthly from 12 months (pre) to 18 months of age (post). This will utilize the CUFFS method (McArdle, 1988) of estimating growth in latent variables.

Analysis 1.2a. Intervention will predict the slope factor in a latent growth curve model of child prelinguistic communicative acts from a language sample from 12 months (pre) to 18 months of age (post). This will be accomplished by including intervention as a predictor in the child prelinguistic communicative acts growth curve.

Analysis 1.2b. CSBS Total Scaled Scores at 18 months of age (post) will be regressed on intervention status controlling for CSBS Total Scaled Scores at pre-test and other relevant covariates.

Aim 2 Analyses

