Analysis 2.3a. Intervention effects on a latent slope representing growth in child prelinguistic communicative acts from a monthly language sample from 12 months (pre) to 18 months of age (post) will be moderated by child attention to spoken language (orienting time toward speech from a sequential looking preference procedure) at 12 months of age (pre). Like analysis 2.2a, this model will be estimated using SEM due to the latent child growth outcome.

Analysis 2.3b. Intervention effects on observed CSBS Total Scaled scores at 18 months (post) will be moderated by child attention to spoken language (orienting time toward speech from a sequential looking preference procedure) at 12 months of age (pre). Like analysis 2.2b, this analysis will be carried out jointly using regression methods for assumption checking and SEM for robust estimation of final parameters.

Aim 3 Analyses

This aim tests the long-term effects of the intervention, both on parental use of communication support strategies and on child spoken language outcomes. We predict that: (a) parents in the intervention group will use more communication support strategies after intervention than parents in the control group (analysis 3.1); (b) children in the intervention group will have greater growth in spoken words between 18 months (post) and 36 months (follow-up) (analysis 3.2a) and greater overall spoken language outcomes at 36 months of age (follow-up) (analysis 3.2b) than children in the control group. As in Aim 1, we will employ a mix of traditional and advanced statistical methods, balancing simplicity of linear regression and related methods with sophisticated SEMs that handle attrition and missing data and allow for more flexible integration of time-varying covariates.

Aim 3 analytic plan. Analyses for Aim 3 will again utilize SEM for both regression and latent growth curve models, with the same benefits to attrition and estimation. The analyses here largely mirror those in Aim 1, looking at long-term rather than short-term intervention effects.

Analysis 3.1. Intervention will predict the slope factor in a latent growth curve model of overall parent use of communication support strategies, which is a latent variable of parent use of communication support strategies estimated monthly from 18 months (post) to 36 months of age (follow-up). This will utilize the CUFFS method⁸⁹ of estimating growth in latent variables.

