Analysis 3.2a. Intervention will predict the slope factor in a latent growth curve model of child spoken language outcomes (a latent variable of total number of different words said from the MCDI and total number of different spoken words from a language sample) from 18 months (post) to 36 months of age (follow-up). This will be accomplished by including intervention as a predictor in the child spoken word growth curve.

Analysis 3.2b. Intervention will predict PLS-5 Standard Scores at 36 months via multiple regression. We will test PLS-5 Standard Scores controlling for pre-test scores as we did in Analysis 1.2b.

Aim 4 Analyses

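### SAP age labels (12, 18, 36 months) do not match the protocol's visit schedule, and age at T0 is not a committed covariate of the raw-count growth models (minor)

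*SAP*

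**What the plan says.** SAP Table 1 schedules the parent-strategy measures "Monthly from 12 to 18 months of age (6 time points between pre and post" and the CSBS "At 18 months of age (post". It places PLS-5 at 36 months. The Aim 1 to 4 text repeats these ages. The example growth curve runs "from age 12 months (C_{12}) to age 18 months (C_{18"; Analysis 1.2b states that "CSBS Total Scaled Scores at 18 months of age (post) will be regressed on intervention status"; and the parent construct in Analysis 3.1 is "estimated monthly from 18 months (post) to 36 months of age (follow-up".

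The protocol works in months since baseline. Section 3.0 admits children with hearing loss at 12 to 18 months of age. Section 8.0 puts post at T7, seven months after baseline, and follow-up at T24.

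The SAP's Covariates paragraph lists variables to be compared between arms, beginning "non-verbal cognitive skills, degree of hearing loss in the better ear, hearing age, hours of hearing device use". Hearing age is there; chronological age is not. The entry rule is "Should a difference exist at any point in the study, we will include that variable in all statistical analyses". Protocol 8.0 says that date of birth is collected so that age can be used in analyses, but the wording is permissive and names no model. Randomisation is stratified by hearing device and communication mode only.

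For Aim 3, Analysis 3.2a opens with "Intervention will predict the slope factor in a latent growth curve model of child spoken language outcomes".

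**The concern.** An age label that no eligible child can meet invites the question of what the time axis is: the child's age, or months since baseline. The two differ by up to six months between children.

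The practical issue is entry age. Two of the monthly outcomes are raw counts: prelinguistic acts, and words (said on the MCDI, and different roots in the language sample). A child entering at 18 months may well be on a different part of the developmental curve from one entering at 12 months. If entry age predicts growth rate, that variation sits in the residual unless age is modelled. Under the SAP's rule a listed variable enters only when the arms differ, and age is not listed. CSBS and PLS-5 are analysed as scaled or standard scores, so the point does not extend to them in the same way.

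A smaller, related matter concerns Aim 3. Its first occasion follows the intervention, so the arms may already differ in level. The text should then say whether arm predicts the intercept as well as the slope.

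**Working it through.** **1. Can the SAP's ages be reproduced?** Age at visit = age at T0 + months since baseline, with age at T0 of 12 to 18 months (Protocol 3.0) and visit months from Protocol 8.0.

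| Visit | SAP age | From the protocol |
|---|---|---|
| Pre, T0 | 12 | 12 to 18 |
| Post, T7 | 18 | 12+7 = 19 to 18+7 = 25 |
| Follow-up, T24 | 36 | 12+24 = 36 to 18+24 = 42 |

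The post age cannot be reproduced. Protocol 8.0 allows a 10-day assessment window without giving its direction. Taken as 10 days early for a child enrolled at exactly 12 months, post would fall at about 18.7 months, still not 18. If post were at month 6, when the intervention ends, the range would be 18 to 24 months, and the label would fit only a child enrolled at exactly 12 months. The follow-up label likewise fits only that child.

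**2. Which visits are analysed?** Each SAP age is paired with pre, post or follow-up, and Protocol 8.0 defines those terms as T0, T7 and T24. Protocol Table 1 gives the CSBS only at T0 and T7, and PLS-5 at T0, T7 and T24. Protocol 1.0, aim (c), gives the long-term window as T7 to T24. The visits are settled; only the labels are wrong.

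**3. What does omitting age at T0 cost?** Let r be the correlation of age at T0 with the true slope, and f the share of the variance of the estimated slope that is error. Neither is in the documents, so both are assumed. Adjusting for age removes a fraction r²(1−f) of that variance, so

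SE ratio (unadjusted / adjusted) = 1/√(1 − r²(1−f)).

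| | r = 0.1 | r = 0.3 | r = 0.5 |
|---|---|---|---|
| f = 0 (upper limit) | 1.005 | 1.048 | 1.155 |
| f = 0.5 | 1.003 | 1.023 | 1.069 |
| f = 0.8 | 1.001 | 1.009 | 1.026 |

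Example: r = 0.3, f = 0.5 gives 1/√(1 − 0.09×0.5) = 1/√0.955 = 1.023. The equivalent loss of children is 96·r²(1−f). At f = 0.5 this is 0.5, 4.3 and 12.0 children.

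The formula ignores the cost of estimating one more coefficient. With 96 children that cost is roughly √(93/92) = 1.005 on the SE. The net ratio at f = 0.5 is therefore about 1.003/1.005 (no gain) at r = 0.1, 1.023/1.005 = 1.018 at r = 0.3 and 1.069/1.005 = 1.064 at r = 0.5. A simulation of 6,000 trials (n = 96, visits T0 to T7, entry age uniform on 12 to 18 months, f = 0.5) gave 1.013 at r = 0.3 and 1.065 at r = 0.5.

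**4. Bias.** Age at T0 precedes randomisation, so its expected difference between arms is zero. Omitting it does not bias the arm contrast.

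**5. Aim 3 and the time origin.** Let b_i and b_s be the arm differences in level and slope, and V_ii and V_is the within-arm intercept variance and intercept-slope covariance. If arm is placed on the slope alone, the fitted contrast is approximately b_s − (V_is/V_ii)·b_i. Moving time zero changes V_is, V_ii and b_i, so the contrast moves too. If both factors are regressed on arm, the contrast is b_s on any origin. The documents give none of these quantities, so no size or direction can be attached.

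**The case against.** The strongest reply is that this is a wording matter. The ages are shorthand for T0, T7 and T24, and nobody analysing the trial would pick the wrong visit. That stands. It disposes of the inference a reader might draw that the wrong assessment would be analysed.

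A reader might also infer that the window containing T7 is unclear, because the example curve labelled 12 to 18 months has seven monthly ages while T0 to T7 has eight visits, and from there compute a penalty for a fit that leaves out the post visit. The documents do not support this. Aim 1 is stated as pre to post and Aim 3 as post to follow-up, so T7 ends one window and opens the other; the seven-label curve is offered only as an example. Nor can the plan be faulted for lacking time scores, since the SAP refers to growth-model figures that were not available to this review.

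For Aim 3, a reader might infer that the slope contrast is distorted by a definite amount. That needs a slope-only model. Analysis 3.1 mentions only the slope, but the sentence following the opening of Analysis 3.2a makes intervention a predictor in the growth curve without that limit. Any figure would also hinge on an assumed intercept-slope correlation, and a different value can reverse which origin looks safe. Only the request for clarification survives.

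On age, it can be said that the protocol collects date of birth for this purpose, and that the SAP's references to other relevant covariates (Analysis 1.2b) and to relevant covariates in the mediation models leave room for it. Room is not commitment: no passage names age at T0 for any model. The reply that the gain may be small is correct.

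**Conclusion.** The age labels contradict the protocol schedule. No eligible child is 18 months old at post, and only a child enrolled at exactly 12 months is 36 months old at T24. This is a labelling error with no demonstrated effect on which data are used.

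What remains is a modest, essentially free improvement in precision for the raw-count growth models. With half of the slope variance being error, omitting age at T0 enlarges the SE by about 0.3%, 1-2% or 7% for an age-slope correlation of 0.1, 0.3 or 0.5. At 0.1 it is not worth having; at 0.5 it is worth about 12 of 96 children. The size rests wholly on these two assumed quantities.

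There is no bias, and the stated regression power figures are unaffected. The growth-model power (80% at d = .34) cannot be adjusted for this, because the simulation inputs are not given. A reader should not infer that the Aim 1 or Aim 3 results would be invalid. Severity: minor.

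**What to change.** 1. Prespecify age at T0, in months, as a covariate of the intercept and slope factors in the models that use raw-count growth (1.2a, 2.2a, 2.3a, 3.2a, 4.1a, 4.2a, 4.3a and 4.3b), whether or not the arms differ on it.
2. In SAP Table 1 and the Aim 1 to 4 text, replace the ages with T0, T7 and T24: CSBS at T7, PLS-5 at T24, Aim 1 growth over T0 to T7 and Aim 3 growth over T7 to T24, with time in months since baseline.
3. As a clarification, state that in Aim 3 both the intercept and the slope are regressed on arm, so that the slope contrast does not depend on the time origin.

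The cost is SAP wording and one baseline covariate, calculated from the date of birth already collected. No new data, visits or participants are needed. The statistical cost is one extra coefficient per growth factor, about 0.5% on the SE by the approximation above.
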